2.1 Arm A objectives

- This is a prospective study which aims to define the clinical characteristics of SARS-CoV-2 infection in cancer patients. The aim is to collect clinical data, throat/nose swabs, saliva and blood longitudinally to investigate viral clearance and seroconversion.

2.2 Arm B objectives

- The arm of the study will investigate the prevalence of SARS-CoV-2 antibodies amongst patients with cancer. Clinical data and blood samples will be collected longitudinally to assess the impact of systemic therapy on SARS-CoV-2 antibody titres.

In parallel, the study will also evaluate an antigen (Arm A) and IgG/IgM antibody (Arms A & B): point of care test (lateral flow assay) for the development of rapid detection of SARS-CoV-2.

3. Study Methods

3.1 Study design

Patients with suspected acute COVID-19 infection will be recruited to Arm A. Throat/nose swabs, saliva and blood will be collected from patients undergoing investigation for suspected SARS-CoV-2 infection at the Royal Marsden NHS Foundation Trust on Day 0 (D0). Patients who are positive for SARS-CoV-2 by throat/nose RT-PCR or have a high clinical suspicion for acute COVID-19 will have further samples collected on D7 (if an inpatient), D14, D28, D42 and D56.

Asymptomatic patients with no clinical suspicion of COVID-19 will be recruited to Arm B. Blood will be collected from patients who do not have symptoms of COVID-19. Repeat blood will be collected on D28, D56 and D84.

Research tests including serology and antigen/antibody lateral flow tests will be performed at St George's University NHS Trust. Exploratory analyses including, but not limited to HLA-KIR profiling, blood immune cell activation and transcriptome and lateral flow testing will be carried out. Viral and immunological data will be collated in a link-anonymised manner and correlated to clinical outcome data. Samples will also be used to develop more rapid SARS-CoV-2 testing and assist in the future planning of ongoing or delayed treatment in cancer patients.

3.2 Sample Size

In Arm A, up to 60 patients with confirmed diagnosis of SARS-CoV-2 by RT-PCR will be recruited over the study period. In Arm B, up to 150 patients with no clinical suspicion of COVID-19 will be recruited.

4. Statistical Principles

4.1 Confidence Intervals and P values

No formal statistical hypothesis testing will be undertaken. All confidence intervals presented will be 95% and two-sided.

4.2 Adherence and protocol deviations

Protocol deviations will be reported as recorded on the relevant CRF.

4.3 Analysis populations

The analysis of the endpoints will involve the following populations:

- ***Patients with a completed blood test (Arm B)***

This population includes all patients who completed at least one blood test during the study.

- ***Unvaccinated patients (Arm B)***

This population includes all patients who did not receive a vaccine dose prior or during their last completed blood test in the study.

- ***Vaccinated patients (Arm B)***

This population includes all patients who received at least one vaccine dose prior to their D0 blood test.

- ***Vaccinated patients with a second dose (Arm B)***

This population includes all patients who received their second vaccine dose after their D0 blood test and prior to their last blood test in the study.

5. Study Population

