6.2 Secondary endpoints

6.2.1 Unvaccinated patients

- Proportion of participants at each timepoint with a positive detection of IgG specific antibodies to SARS-CoV-2 (nucleocapsid and spike-protein).
- Geometric fold rise (GMFR) in geometric concentration (GMC) of spike-protein antibodies from the first timepoint with a positive antibody detection to each following timepoint, in antibody positive patients. If data required to analyse this endpoint is not available at the time of primary analysis, the analysis for this endpoint will be postponed until the data is provided.

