6.2.2 Vaccinated patients

- Proportion of participants at each timepoint with a positive detection of (i) IgG specific antibodies to SARS-CoV-2 (spike-protein) and (ii) pseudovirus neutralisation. As part of a sensitivity analysis, proportions will be reported at each timepoint to include only patients who had not received a positive nucleocapsid detection up to and including that timepoint.

- Proportion of participants with a positive detection of (i) IgG specific antibodies to SARS-CoV-2 (spike-protein) and (ii) pseudovirus neutralisation at time periods adjusted to the no. of days from 1st vaccine date. As part of a sensitivity analysis, proportions will be reported at each time period to include only patients who had not received a positive nucleocapsid detection up to and including that time period.
- Geometric fold rise (GMFR) in geometric concentration (GMC) of spike-protein antibodies from the D0 sample timepoint to each post-D0 timepoint. If data required to analyse this endpoint is not available at the time of primary analysis, the analysis for this endpoint will be postponed until the data is provided.

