6.3.3 Other exploratory endpoints

The following endpoints are also planned to be performed:

- Investigate antigen dynamics over time to compare with quantitative RT-PCR (Arm A)

- To examine HLA-KIR interactions that shape CD8 anti-viral responses (Arms A & B)
- To explore the relationship between host immune genotype (e.g., HLA-KIR) and peripheral blood (Arms A & B) immune cell phenotype with viral clearance (Arms A & B)
- To investigate blood immune cell activation and transcriptome in participants (Arms A & B)

Due to the rapidly evolving nature of the COVID-19 pandemic, these exploratory endpoints are no longer relevant to this study. As the focus of the study has shifted towards exploring the serological responses following SARS-CoV-2 infection or vaccination (1,2), these exploratory endpoints will no longer be performed.

7. Analysis methods for endpoints

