7.2 Secondary endpoints

7.2.1 Unvaccinated patients

- At each sample timepoint (D0, D28, D56, D84), the proportion of patients with a positive detection of (i) nucleocapsid antibodies and (ii) spike-protein antibodies will be reported alongside an exact two-sided 95% confidence interval.
- *Geometric fold rise (GMFR) in geometric concentration (GMC) of spike-protein antibodies from the first timepoint with a positive antibody detection to each following timepoint, in antibody positive patients.* A scatterplot will be produced to plot the GMFR in GMC of antibodies against sample timepoints (D0, D28, D56, D84) in antibody positive patients. For each patient, the first data point to be plotted will be at the first sample timepoint at which they showed a positive antibody detection.

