7.2.2 Vaccinated patients

- For all patients who received at least one dose prior to D0, at each sample timepoint (D0, D28, D56, D84), the proportion of patients with a positive detection of (i) spike-protein antibodies and (ii) pseudovirus neutralisation will be reported alongside exact two-sided 95% confidence intervals. For the sensitivity analysis, the proportions will be reported in a similar manner except the denominators and numerators used to calculate each proportion will only include patients who had not received a positive nucleocapsid detection up to and including that timepoint.
- At each time period (adjusted to the no. of days from 1st vaccine date), the proportion of patients with a positive detection of (i) spike-protein antibodies and (ii) pseudovirus neutralisation will be reported alongside an exact two-sided 95% confidence interval. For the sensitivity analysis, the proportions will be reported in a similar manner except the denominators and numerators used to calculate each proportion will only include patients who had not received a positive nucleocapsid detection up to and including that timepoint.

- *Geometric fold rise (GMFR) in geometric concentration (GMC) of spike-protein antibodies from the D0 sample timepoint to each post-D0 timepoint.* A scatterplot will be produced to plot the GMFR in GMC of spike-protein antibodies against sample timepoints (D0, D28, D56, D84). For each patient, the first data point to be plotted will be at their D0 sample timepoint.

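### SAP 4.3 dates vaccinated status by the D0 draw and unvaccinated status by the last draw, so patients first dosed in between are in neither group and their pre-dose samples drop out of the unvaccinated results

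*SAP*

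**What the plan says.** SAP 4.3 sets three vaccination-based populations for Arm B:

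- Unvaccinated: "This population includes all patients who did not receive a vaccine dose prior or during their last completed blood test in the study".
- Vaccinated: "This population includes all patients who received at least one vaccine dose prior to their D0 blood test". SAP 7.2.2 repeats the D0 anchor: "For all patients who received at least one dose prior to D0, at each sample timepoint".
- Vaccinated with a second dose: "all patients who received their second vaccine dose after their D0 blood test and prior to their last blood test in the study". The timing of the first dose is not given.

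The unvaccinated population carries the by-visit proportions and the spike fold rise, the latter taken "from the first timepoint with a positive antibody detection to each following timepoint, in antibody positive patients" (SAP 6.2.1 and 7.2.1). It is also one stratum of the sensitivity and specificity results, which are reported for vaccinated, unvaccinated and all patients (SAP 6.3.1 and 7.3.1). The vaccinated population has by-visit results and a second analysis "at time periods adjusted to the no. of days from 1st vaccine date" (SAP 6.2.2 and 7.2.2). Arm B blood is drawn at D0, D28, D56 and D84 (Protocol 9.3 and Table 3).

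**The concern.** The two main definitions look at different dates. A patient who is undosed at D0 and has a first dose by the last draw fails both, and nothing else in the SAP assigns that patient or keeps the samples drawn before the dose.

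Membership of the unvaccinated group at an early visit is therefore decided by later events. Take two patients first dosed on day 40. The one whose last draw was D28 counts as unvaccinated; the one who stayed to D56 or D84 does not, although both gave undosed samples at D0 and D28.

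Two further things are at stake. The vaccinated and unvaccinated strata need not add up to the all-patient sensitivity/specificity total, and the flow diagram in SAP 5.1 would not show why, because it tracks exclusions from the primary analysis only. Also, under these definitions the unassigned patients are the only ones who can be sampled on both sides of a first dose. SAP 6.3.3 says that "the focus of the study has shifted towards exploring the serological responses following SARS-CoV-2 infection or vaccination", so their handling should be stated.

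**Working it through.** **1. Applying the definitions.** Vaccinated requires first dose before the D0 draw. Unvaccinated requires no dose before or during the last completed draw.

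| First dose | Last draw | Vaccinated | Unvaccinated | Pre-dose draws left out of the unvaccinated results |
|---|---|---|---|---|
| Day 0, after the draw | D0 or later | no | no | D0 |
| Day 10 | D28, D56 or D84 | no | no | D0 |
| Day 40 | D28 | no | yes | none |
| Day 40 | D56 or D84 | no | no | D0, D28 |
| Day 70 | D56 | no | yes | none |
| Day 70 | D84 | no | no | D0, D28, D56 |

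No pattern falls in both populations. A same-day dose is treated differently at the two ends: it is not prior to D0, yet it counts as during the last draw. So a patient whose only draw is D0 and who is dosed that day after the draw is also in neither. D84 unvaccinated results are affected only if a dose is given on the day of the D84 draw, after the blood is taken.

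Read literally, the second-dose population takes in some of these patients (for example, doses on days 10 and 40 with last draw D84). It reports only fold rises from the last sample before the second dose (SAP 6.3.2 and 7.3.2), so it returns nothing to the unvaccinated results.

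**2. The plan's own precision figure.** Protocol 14.1 gives ±4.8% for 150 patients at 10% positive: 1.96 × √(0.1 × 0.9 / 150) = 0.0480. It reproduces.

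**3. Assumed illustration of size.** The documents give no uptake, drop-out or vaccination counts. Assume drop-out d = 10% per 28 days, independent of dosing, and first-dose uptake h per 28 days among patients undosed at D0. With k = 0, 1, 2, 3 for last draw D0, D28, D56, D84:

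- P(last = k) = 0.100, 0.090, 0.081, 0.729.
- Kept as unvaccinated = Σ P(last = k)(1 − h)^k. In neither population = 1 − kept.
- Left out at visit v = 1 − [Σ over k ≥ v of P(last = k)(1 − h)^k] / [P(last ≥ v)(1 − h)^v].

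For h = 10%: kept = 0.100 + 0.081 + 0.0656 + 0.5314 = 0.7781. For h = 2%: 0.100 + 0.0882 + 0.0778 + 0.6861 = 0.9521.

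| Uptake h | In neither (same as D0 samples left out) | D28 pre-dose samples left out | D56 pre-dose samples left out |
|---|---|---|---|
| 2% | 4.8% | 3.4% | 1.8% |
| 5% | 11.6% | 8.3% | 4.5% |
| 10% | 22.2% | 16.3% | 9.0% |

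Changing drop-out from 0% to 20% moves the in-neither share from 5.9% to 3.8% at h = 2%, and from 27.1% to 17.9% at h = 10%.

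**4. Precision at D0.** As an upper bound on the base, let all 150 be undosed at D0. Then n = 150 × 0.9521 = 142.8 gives 1.96 × √(0.09 / 142.8) = ±4.9 points, and n = 150 × 0.7781 = 116.7 gives ±5.4 points.

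**5. Fold rise.** A patient loses a value only with two or more pre-dose draws and a positive before the last of them. Two or more pre-dose draws: P(last ≥ D56)(1 − h)h + P(last = D84)(1 − h)²h. At h = 10% this is 0.81 × 0.09 + 0.729 × 0.081 = 13.2 per 100 undosed at D0; at h = 2% it is 3.0 per 100. At a constant 10% positivity, about 1.3 and 0.3 per 100 lose a value.

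**6. Effect on the follow-up mix, h = 10%.** With independent drop-out of 10%, incomplete follow-up makes up (0.7781 − 0.5314) / 0.7781 = 31.7% of the D0 unvaccinated set, against 1 − 0.729 = 27.1% of all pre-dose D0 samples. Suppose instead that drop-out is 20% per interval in patients due to be dosed within 84 days and 0% in others. The shares are then (0.1 × 0.2 + 0.09 × 0.36 + 0.081 × 0.488) / (0.729 + 0.0919) = 11.2%, against 0.271 × 0.488 = 13.2%. The mix can move either way.

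**The case against.** The strongest reply is that little is shown to be lost. The number affected is unknown. SAP 4.1 rules out hypothesis testing. The primary endpoint (SAP 6.1 and 7.1), the all-patient sensitivity/specificity results and the pseudovirus descriptives (SAP 6) all keep these patients. This stands, and it limits the importance of the point.

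The second reply is that never-vaccinated against vaccinated-at-entry is a coherent contrast with no overlap, and that new vaccination does not change who is in the unvaccinated set from visit to visit. This also stands as an argument for keeping the SAP's set. It does not answer the conditioning on later events, nor the silence on where the remaining patients go. Reporting both sets meets it.

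Third, the illustration rests wholly on assumed rates, and its base of 150 undosed patients is unlikely, since the SAP sets endpoints for patients vaccinated before D0. That is correct: the figures show a scale, not an estimate.

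A reader might infer that the unvaccinated antibody proportions are biased, or that on-study vaccinees are lost from the study. The documents support neither. No information links antibody status to later dosing, and the follow-up mix can shift in either direction. Nor is the days-from-first-vaccine analysis simply silent: it sits under the vaccinated heading, so by default it excludes patients first dosed on study. Only the missing D0 qualifier in its own bullet leaves some doubt.

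**Conclusion.** The gap in SAP 4.3 is real and follows from its wording alone. Patients first dosed on study by their last draw are in neither population, valid pre-dose samples are left out, and the D0, D28 and D56 unvaccinated results depend on later dosing and length of follow-up. D84 is touched only by the same-day case.

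The size is not known from the documents and may be zero. Under assumed 10% drop-out and 2% to 10% uptake per 28 days, about 5% to 22% of patients undosed at D0 would be unassigned. Even with all 150 undosed at D0, the half-width moves only from ±4.8 to between ±4.9 and ±5.4 points. The primary endpoint is untouched. This is an inexpensive improvement to descriptive secondary and exploratory results, not a flaw that threatens the study's main result.

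**What to change.** 1. Report the unvaccinated proportions, fold rise and sensitivity/specificity using every sample drawn before the patient's first dose, censored at that dose, alongside the SAP's never-vaccinated set. Either may lead, provided the choice is fixed before analysis. State one rule for a dose on the day of a draw and apply it at every visit.
2. For the days-from-first-vaccine analysis, either include the post-dose samples of patients first dosed on study or state that they are excluded. State whether the second-dose population is limited to patients first dosed before D0.
3. For sensitivity/specificity, classify by dose status at the draw, under a label distinct from the pre-D0 vaccinated population, or show unassigned patients as a separate row.
4. Report the number first vaccinated on study.

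The cost is SAP wording and re-coding from vaccine dates that SAP 4.3, 6.2.2 and 7.2.2 already require; no new data are needed. The downside is that the make-up of the unvaccinated group then changes by visit, so trends across visits need cautious reading. The never-vaccinated set is the check on that.

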
e: Two samples will be taken, one for diagnostic testing and one for research purposes and storage for further analysis.

f: For collection of serum and whole blood. See laboratory manual for full details

g: See laboratory manual for collection details.

Arm B:

Blood

Approximately 30mL of blood will be taken at each study visit (D0, D28, D56, D84). The blood samples taken are outlined in Table 3.

Table 3. Schedule of assessments (Arm B)

Assessment	D0	D28 +/- 10 days	D56 +/- 10 days	D84 +/- 10 days
Informed consent	X			
Registration	X			
Patient demographics	X			
Medical history ^a	X			
Concomitant medications	X			
Symptom assessment ^b	X	X	X	X
Blood (serum and EDTA whole blood) ^b	X	X	X	X

Schedule of Assessments Table Key

a: Includes past medical history, oncological history

b: See laboratory manual for full details

12. Study Organisation/ Trial Monitoring and Management Strategy

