6.3.2 Vaccinated patients with a second dose

- Geometric fold rise (GMFR) in geometric concentration (GMC) of spike-protein antibodies from baseline (pre-second dose) to each timepoint (post-second dose). If data required to analyse this endpoint is not available at the time of primary analysis, the analysis for this endpoint will be postponed until the data is provided.
- GMFR of neutralising geometric mean titres (GMT) of spike-protein antibodies from baseline (pre-second dose) to each timepoint (post-second dose). If data required to analyse this endpoint is not available at the time of primary analysis, the analysis for this endpoint will be postponed until the data is provided.

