7.3.2 Vaccinated patients with a second dose

- *Geometric fold rise (GMFR) in geometric concentration (GMC) of spike-protein antibodies from baseline (pre-second dose) to each timepoint (post-second dose).* A scatterplot will be produced to plot the GMFR in GMC of spike-protein antibodies against sample timepoints (D0, D28, D56, D84). For each patient, the first data point to be plotted will be at the last sample timepoint prior to their second dose.
- *GMFR of neutralising geometric mean titres (GMT) of spike-protein antibodies from baseline (pre-second dose) to each timepoint (post-second dose).* A scatterplot will be produced to plot the GMFR in GMT of spike-protein antibodies against sample timepoints (D0, D28, D56, D84). For each patient, the first data point to be plotted will be at the last sample timepoint prior to their second dose.

The number and proportion of patients with major and minor protocol deviations, alongside deviation details will be reported.

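### The second-dose population does not require a first dose before the baseline sample, so the exploratory second-dose fold rise could include first-dose response

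*SAP*

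**What the plan says.** SAP 4.3 sets out three vaccination-based populations in Arm B, each with its own free-standing rule:

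- Unvaccinated: patients who "did not receive a vaccine dose prior or during their last completed blood test in the study".
- Vaccinated: "This population includes all patients who received at least one vaccine dose prior to their D0 blood test".
- Vaccinated with a second dose: patients who "received their second vaccine dose after their D0 blood test and prior to their last blood test in the study".

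The third rule dates the second dose only and is silent on the first. It does not say that the set is drawn from the Vaccinated population; only its label suggests that.

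SAP 6.3.2 defines two exploratory fold rises in this population, one for spike-protein antibody concentration and one for neutralising titre. Both run "from baseline (pre-second dose) to each timepoint (post-second dose"). SAP 7.3.2 makes the baseline operational for each patient: "the first data point to be plotted will be at the last sample timepoint prior to their second dose". The baseline is therefore not always D0, and it is not required to come after the first dose.

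The Arm B schedule (Protocol 9.3 and Table 3 in 11.2) takes blood on D0, D28, D56 and D84, with a window of 10 days either side of each visit after D0.

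**The concern.** A fold rise from before to after the second dose is informative about that dose only if the baseline already reflects the first. As written, a patient unvaccinated at one sample who has both doses before the next available sample meets the membership rule. That patient's baseline is a pre-vaccination sample, so the ratio measures two doses but is reported as the response to one.

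The protocol does not close this route: it has no exclusion criteria (Protocol 8.3), so patients may enter Arm B unvaccinated. The SAP expects doses during follow-up, because its Unvaccinated rule runs to the last completed blood test. It also expects missing samples, because the primary endpoint has a complete-case sensitivity analysis (SAP 6.1 and 7.1).

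At stake is the meaning of the two fold rises in SAP 6.3.2. Pooling two-dose ratios with one-dose ratios would be expected to push the GMFR upward.

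**Working it through.** The plan gives no sample size, precision or expected fold rise for the second-dose population, so there is no figure of its own to reproduce.

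**1. Apply the rules to possible sequences.**

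| Sequence | Literal rule | Subset of Vaccinated | Baseline |
|---|---|---|---|
| dose 1, D0, dose 2, sample | in | in | after dose 1: valid |
| D0, dose 1, sample, dose 2, sample | in | out | after dose 1: valid |
| D0, dose 1, dose 2, sample | in | out | before dose 1: two-dose ratio |

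The two readings give different datasets, and only the third row is a problem. Patients in the second and third rows belong to neither the Vaccinated nor the Unvaccinated population. The second-dose set is the only vaccination subgroup they can enter.

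**2. How far apart can two samples be?** From Table 3, D0 is day 0, D28 falls on days 18 to 38, D56 on days 46 to 66, and D84 on days 74 to 94.

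| Pair | Visits missed | Nominal gap | Smallest gap | Largest gap |
|---|---|---|---|---|
| D0 to D28 | 0 | 28 | 18 | 38 |
| D28 to D56 | 0 | 28 | 46 − 38 = 8 | 66 − 18 = 48 |
| D56 to D84 | 0 | 28 | 74 − 66 = 8 | 94 − 46 = 48 |
| D0 to D56 | 1 | 56 | 46 | 66 |
| D28 to D84 | 1 | 56 | 74 − 38 = 36 | 94 − 18 = 76 |
| D0 to D84 | 2 | 84 | 74 | 94 |

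Both doses fit inside a gap only if the dose interval is shorter than that gap.

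**3. How often might that happen?** The documents give no dose interval, so it has to be assumed. Suppose the second dose falls uniformly within a gap of G days, the dose interval is d days, and the first-dose date is not otherwise restricted. Then the first dose lies in the same gap with probability max(0, 1 − d/G):

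- G = 28 (nominal): d = 14 gives 50%, d = 21 gives 25%, d = 28 or more gives 0%.
- G = 48 (longest gap with no missed visit): d = 28 gives 1 − 28/48 = 42%, d = 42 gives 12.5%, d = 56 gives 0%.
- G = 56 (nominal, one missed visit): d = 28 gives 50%, d = 42 gives 25%, d = 56 gives 0%.
- G = 84 (nominal, two missed visits): d = 56 gives 33%, d = 70 gives 17%, d = 84 gives 0%.

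These shares apply to patients whose second dose falls in that particular gap, not to the whole population. They show that the answer runs from zero to substantial, depending on an interval the documents do not state.

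**4. Effect on the GMFR.** Let r be the true second-dose ratio, f1 the multiple due to the first dose alone, and q the affected share. The mean log ratio is (1 − q) log r + q log(r × f1) = log r + q log f1, so the GMFR becomes r × f1^q.

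- q = 0: multiplier 1.00 for any f1.
- q = 10%: 5^0.10 = 1.17; 10^0.10 = 1.26.
- q = 25%: 5^0.25 = 1.50; 10^0.25 = 1.78.

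Both q and f1 are assumed. The formula also takes r to be the same in affected and unaffected patients.

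**5. After the fix.** Requiring the first dose before the baseline sample makes q = 0 and the multiplier 1.00.

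**The case against.** The strongest reply is that the label already settles the matter. Vaccinated patients is a defined term meaning a dose before D0, and the next population repeats the term and adds a second-dose date. On that reading every first dose precedes D0, every baseline sample follows it, and the problem disappears. The layout of SAP 4.3 lends support: a plan that leaves patients first dosed after D0 out of both main groups may not have meant to admit them here.

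That reading is plausible, but the text does not state it. The rule is worded to include all patients meeting the second-dose condition. The neighbouring population writes out the pre-D0 dose, and SAP 7.2.2 repeats that condition for its first analysis; SAP 7.3.2 does not. Two programmers could reasonably build different sets.

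Other parts of the reply stand:

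- The route is narrow. A first dose after D0 does no harm if any sample falls between the doses.
- With a dose interval of 48 days or more and no missed visits, no patient can be affected. At the nominal 28-day spacing, a 28-day interval also gives none.
- The sizes above rest on assumed inputs, because the documents give no vaccination dates, dose interval or number in this population.
- The endpoints are exploratory, the SAP plans no hypothesis testing (4.1), and the only output that 7.3.2 specifies for them is a scatterplot.

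**Conclusion.** The gap in the wording is real, and its consequence is limited. On the literal rule, a fold rise labelled as second-dose response can include patients measured from a pre-vaccination baseline. The number of such patients cannot be derived from the documents and may be zero. The multiplier on the GMFR is 1.00 if nobody is affected, and 1.17 to 1.26 if 10% are affected and the first dose alone raises the level 5- to 10-fold, both figures being assumptions.

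A reader might infer more: that the second-dose GMFR is known to be inflated by a set amount, or that a few very low baselines would dominate it. The documents support neither. They do not show how the set will be coded or when anyone was vaccinated. In the arithmetic above, one patient in ten with a tenfold larger ratio moves the geometric mean by a factor of 1.26, which is an upward shift rather than dominance.

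The primary endpoint is not touched. Nor is the secondary fold rise in Vaccinated patients, whose first dose precedes their D0 baseline by definition. This is an inexpensive clarification worth making, not a flaw in the study's main results.

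**What to change.** In SAP 4.3 and 7.3.2, state that:

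1. the fold-rise analyses of 6.3.2 include only patients whose first dose preceded the baseline sample, with baseline defined as the last sample after the first dose and before the second;
2. the second-dose population is, or is not, meant to be a subset of the Vaccinated population;
3. the number of patients excluded for having no sample between doses will be reported.

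Item 1 narrows the literal rule and leaves the subset reading unchanged, because there D0 itself lies between the doses. The estimate is then a second-dose ratio whichever reading was intended. Item 2 settles whether patients first dosed after D0, but sampled between doses, belong in the set.

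The cost is a sentence or two in the SAP, plus a first-dose date, which the Vaccinated and Unvaccinated definitions and the days-from-first-vaccine analysis in 6.2.2 already need. The downside is possibly a few fewer patients in an exploratory analysis. If the analysis has already been run, counting and disclosing the affected patients would serve the same purpose.
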